More effective and efficient gingival displacement procedure can lead to clinically improved fixed restorations, less patient chair time, and less patient discomfort.

Materials and Methods: One hundred (100) patients will be recruited from the University of North Carolina (UNC) School of Dentistry (SOD). A stratified block randomization will be used to randomize patient to impression technique: Aquasil Ultra Cordless, Dentsply International using Aquasil Ultra Polyvinyl siloxane (PVS) impression material versus Dentsply International, gingival displacement cord (Ultrapak, Ultradent Products International) hydrated with aluminum chloride hexahydrate (Hemodent, Premier Dental Products Company). Stratification will be based on the clinic where treatment is provided (Dental Faculty Practice, Graduate Operative Dentistry, Graduate Prosthodontic Clinic), A block size of 4 within each stratum will be used to maintain a balanced allocation to impression group. Patient inclusion criteria include: 1) requires indirect restoration 2) probing depths 4mm or less. 3) No bleeding on probing. 4) finish line 0-1mm sub-gingival.

Specific Aims

The intent of this exploratory study is to compare two methods (cordless vs corded gingival displacement) currently used in clinical practice to displace sulcular tissues to facilitate an acceptable dental impression that accurately captures the prepared cervical finish line for the fabrication of indirect fixed prosthodontic restorations. The primary aims are to compare the two methods with respect to 1) the accuracy of the impression with respect to capturing the prepared cervical finish line for the fabrication of the indirect fixed prosthodontic restoration as assessed by two expert clinicians 2) the time required to prepare the impression and 3) the discomfort of the procedure as reported by the patient. Secondary aims are to estimate the effect of clinician experience (resident level vs faculty) and jaw of restoration placement (maxillary vs mandibular) on the outcomes of accuracy, time, and discomfort.

Significance

Indirect fixed prosthodontic restorations are widely used for the restoration of teeth. The fabrication of a well-fitting indirect restoration requires an accurate impression which captures the cervical finish line. Dentists have a hard time making proper impressions, with a reported 56% of impressions sent to labs being inadequate. The most common deficiency is inadequate recording of the cervical finish line. The primary reason for this inadequacy is deficient gingival displacement technique.

The traditional procedure used to displace gingival tissue prior to making impressions is gingival retraction cord, with a reported 92% of dentists surveyed employing this procedure. (Ahmed 2014) For this procedure to work properly, it is time consuming (requires 7-10 minutes in the sulcus), technique sensitive, requires anesthetizing the patient, and causes patient discomfort both during and post operatively.

More effective and efficient gingival displacement procedure can lead to clinically improved fixed restorations, less patient chair time, and less patient discomfort.

The specific aims in this proposal explore whether a cordless gingival displacement procedure can properly displace sulcular tissues to facilitate an acceptable impression that accurately captures the prepared cervical finish line for the fabrication of indirect fixed prosthodontic restorations and thereby improve the efficiency of a traditionally technique sensitive procedure in dentistry.

Methods

A total of one hundred participants will be recruited from the University of North Carolina (UNC) School of Dentistry (SOD) Graduate Prosthodontics clinic, Graduate Operative clinic, and the Dental Faculty Practice. A stratified block randomization will be used to randomize patient to impression technique: Aquasil Ultra Cordless, Dentsply International using Aquasil Ultra Polyvinyl siloxane (PVS) impression material versus Dentsply International, gingival displacement cord (Ultrapak, Ultradent Products International) hydrated with aluminum chloride hexahydrate (Hemodent, Premier Dental Products Company). Stratification will be based on the clinic where treatment is provided (Dental Faculty Practice, Graduate Operative Dentistry, Graduate Prosthodontic Clinic). A block size of 4 within each stratum will be used to maintain a balanced allocation to impression group. The randomization schedule will be prepared by [name]. Randomization allocations will be placed in sequentially numbered envelopes for ease of use by clinicians within the three clinics.

The treating clinician will open the allocation envelope after the tooth preparation is completed. This is to limit the potential bias of the clinician altering the tooth preparation design in anticipation of a known gingival displacement technique. Although the patient may require restorations on multiple teeth, only one tooth, the most posterior, will be included in the evaluation. The clinician will be instructed to

complete the impression for that tooth before proceeding to other teeth. The patient will be informed that participation, if multiple teeth are treatment planned, may increase the appointment time.

The gingival displacement procedures and impression procedures are described here:

Traditional Corded Impression Procedure:

- 1) The prepared tooth is washed and dried, and assure hemostasis.
- 2) Small diameter retraction cord, after it has been hydrated with Hemodent for 10 minutes, is tucked around the tooth in the space between it and its surrounding gum tissue. A second larger diameter retraction cord, also hydrated with Hemodent, will be placed over the first cord and tucked around the tooth. These cords will be left in place for a minimum of 8 minutes. These cords temporarily push the gum tissue back away from the tooth. (Before making the impression, the 2nd larger cord is removed, and the gums will stay back long enough for the impression material to seep around the tooth, thus allowing it to capture a copy of the entire tooth preparation.)
- 3) After a minimum of 8 minutes, the larger 2nd cord will be removed, and the tooth dried. Quickly, after confirmation of a dry field, the light body consistence impression material is syringed around the prepared tooth and across the occlusal surfaces of adjacent teeth.
- 4) An impression tray that has been filled with the heavy body consistency impression material is then placed over the arch of teeth, and gently pressed into place to ensure the teeth are completely covered with a uniform thickness of impression material. As the different impression material consistencies set, they fuse together into a single unit.
- 5) When removed from the mouth, the impression should contain a negative copy of both the prepared tooth and the teeth of that jaw.

Cordless Impression Procedure:

- 1) The prepared tooth is washed and dried, and assure hemostasis.
- 2) Apply B4 + surface optimizer.
- 3a) If 1 prepared tooth requiring an indirect restoration is being impressed, a single size (0.7mL) unit dose cartridge will be inserted into the digit power dispenser. If more than 1 prepared tooth requiring an indirect restoration is being impressed, a multi size (1.6mL) unit dose cartridge will be inserted into the digit power dispenser.
- 3b) Using the digit power dispenser, unit dose cartridge, and intrasulcular mixing tip, depress foot pedal and gently insert tip into the gingival sulcus of the prepared tooth, slightly apical to the preparation finish line. Material should flood the sulcus. Make sure to dispense material ahead of the intrasulcular tip, and completely around the prepared finish line, and then the tooth.
- 4) An impression tray that has been filled with the heavy body consistency impression material is then placed over the arch of teeth, and gently pressed into place to ensure the teeth are completely covered with a uniform thickness of impression material. As the different impression material consistencies set, they fuse together into a single unit.
- 5) When removed from the mouth, the impression should contain a negative copy of both the prepared tooth and the teeth of that jaw.

The clinician will record the impression technique, type of impression material used; whether tray adhesive was used; the tray material; the type of tray used; the number of units requested; the time required to obtain the first impression (start and end of impression taking is defined above for each procedure), and the total number of impressions produced until an adequate impression was made. Also recorded will be the clinic and resident year if placed in a graduate clinic and the subject's age and sex. Unique id numbers not related to clinical record will be used.

The impressions will be photographed, digitally scanned, saved in black and white, and then collectively evaluated at a later time based on a criteria evaluation form by two calibrated evaluators. The evaluators (also referred to as expert examiner) will assess each impression for errors in the finish line; in the tray/material; and errors with gingival displacement/hemostasis as primary outcomes. The number of errors can range from 0 to 13.

Patient discomfort will be assessed using the FACES visual picture pain scale rated from 1-10 based on the following question posed at 4 points during treatment; "How much discomfort are you experiencing at this point in treatment?" This question will be asked at the beginning of the treatment appointment, immediately before the impression procedure is initiated, immediately after the impression procedure is completed, and again at the completion of the treatment appointment. Each question will be rated on a scale of 1 to 10. The total score indicated by the sum of the 4 questions will be analyzed.

Patient consent will be obtained prior to treatment and the impression. This may occur at a prior treatment planning visit or at the treatment visit.

Inclusion Criteria:

- Patients must be adult males or females 18 years of age or older.
- Patients must be able and willing to follow study procedures and instructions.
- Patients must have read, understood and signed an informed consent form.
- Patients must be in good general health, (based on a review of the medical history, blood pressure and heart rate).
- Patients must have no health-related contra-indications to dental treatment.
- Patient must require at least one indirect restorations (crowns).
- Probing pocket depths around the treatment tooth/teeth must be 4mm or less.
- There must be no bleeding on probing around the treatment tooth/teeth.
- The prepared finish line must be between 0 to 1mm sub-gingival (inclusive).

Exclusion Criteria:

- Individuals who have a chronic disease with oral manifestations.
- Individuals who exhibit gross oral pathology.
- Smokers
- Uncontrolled Diabetics (per review of medical history)
- Probing pocket depths around treatment tooth/teeth of greater than 4mm.
- Bleeding on probing around treatment tooth.teeth.
- The prepared finsh line is greater than 1mm sub-gingival.

The inclusion/exclusion criteria limit generalizability of the findings to patients without confounding periodontal or medical issues. However, the sample size of this study is not sufficient to extend to a consideration of the effect of these confounders on the comparison of the two impression techniques.

The proposed research study requires a total of 100 participants. Patients will be recruited from and will be treated in the Dental Faculty Practice, the Graduate Operative Clinic, and the Graduate Prosthodontic Clinic. The patient may seek other dental treatments in the above mentioned clinics or in other clinics in the School of Dentistry.

Study clinicians will be trained and calibrated on both the cordless and the corded gingival displacement procedures and impression procedures in a practice session. Clinical instruction protocols will be printed on laminated forms for all study clinicians to follow, for both the cordless and the corded procedures. These clinical protocol forms will be in the clinicians operatory during actual study treatment, and this protocol must be followed for the impression to be included in the study. The clinical instruction protocol is listed in Appendix A.

In addition to a signed Consent form, the study subject will be asked to complete the standard adult medical and dental health history questionnaire provided by the UNC SOD (Appendix 1) and will be provided with the UNC Chapel Hill Notice of Privacy Practices and the Consent for Purposes of Treatment, Payment and Health Care Operations (Appendix 2). Other than the research consent, these are standard practices followed by UNC SOD for all patients. The study is mandated to adhere to these protocols prior to treating a patient at the UNC SOD. After consent has been obtained, an oral examination will be performed by the treating dentist to confirm the patient meets inclusion criteria. The patient will be dropped from the study if inclusion/exclusion criteria are not met. The treating clinician will record the criteria that resulted in the patient being dropped (See Appendix B). If the inclusion criteria are not met, a clinically appropriate impression method will be performed at the clinician's judgment and will be made per case by the treating clinician, following standard of care.

Customary anesthesia and tooth preparation will be performed by the clinician as necessary for the particular indirect restoration. The gingival displacement procedure and impression will be made as described in this study protocol and as followed on the laminated clinical protocol sheet. If the clinician finds that the first impression is inadequate and chooses to make an additional impression, only the first impression will be evaluated for the study and a note will be indicated to record the number of impressions the clinician made to achieve an acceptable impression.

Patients will be given appropriate verbal and written post-procedure instructions; and appointments will be made for restoration try-in and delivery, as would happen as part of their regular treatment.

There are no potential direct benefits to the participant besides the fact that particularly close attention will be paid to the gingival displacement and impression procedures, and there will be close evaluation of impressions.

All of the impressions will be photographed and digitally scanned, and saved in black and white. These scans will be evaluated collectively on a later day, and will be critiqued based on a criteria form (See Appendix B). This evaluation will be performed by 2 calibrated expert examiners for all impressions, and will be completed independently. If a conflict exists in evaluations between examiners, the examiners will meet to form a consensus response. Impressions will be deemed acceptable or not acceptable, and the reasons for not acceptable impressions will be indicated. The evaluation criteria are listed in Appendix B.

In an effort to reduce bias in reviewing the impressions, all of the images will be black and white so not to clue the examiners into which color of impression material was used, which could be correlated with each technique.

The scientific knowledge to be gained will be the efficacy of a new gingival displacement procedure, and if it can be adopted to improve patient treatment and treatment outcomes.

The risks of the study are consistent with the current standard of care. Standard treatment protocols will be observed for the treatment of teeth which require indirect restorations. The risks will be minimized by

treatment evaluation and proper treatment technique.

Data monitoring

Research data management will involve collection, entry, processing, storage, retrieval, archival, distribution and documentation of information. Data collection will adhere to precise written forms. Data will be stored in a series of Microsoft Access data files, which will be accessible to the Investigators and their staff. Only project-related personnel will be able to access these files. Data collection forms will be kept in locked files. Quality assurance (QA) will occur as data is entered in order to check for data completeness and consistency prior to entry.

Statistical Analysis:

Descriptive statistics for all study variables will be computed by impression group and used to summarize the procedural materials used in the impression and the outcomes. The primary outcomes are the number errors of the impression in the finish line; in the tray/material; and errors with gingival displacement/hemostasis (number of errors can range from 0 to 13), the time to complete the impression, and patient discomfort (range from 0 to 40). Since the outcomes are unlikely to be normally distributed, the Wilcoxon rank sum test will be used as the primary statistical test to assess whether the quality of impressions, time, or patient discomfort made with a cordless gingival displacement procedure is different than with a corded technique. To adjust for additional covariates [clinic providing care, jaw, procedural materials], Poisson regression will be used to assess the relationship between the primary outcomes and the covariates of interest, including impression group with a primary interest in estimation using confidence intervals.

The lack of historical data comparing the proposed outcomes between the two impression groups makes a sample size calculation difficult. For this exploratory study which is time constrained as a thesis project, a sample size calculation was done using an effect size which may be larger than the clinically meaningful effect size. A sample size of 30 in each group will have 80% power to detect a probability of 0.709 that an observation (number of total errors) in the Cordless group is less than an observation in the Corded group using a Wilcoxon (Mann-Whitney) rank-sum test with a 0.05 two-sided significance level.

Budget

Materials	Amount needed	Estimated costs
Aquasil Ultra Cordless Pneumatic Power Dispenser Units (3)	3 systems	Included in normal clinic treatment
Aquasil Ultra Cordless PVS material	Enough for 30 impressions + 10 for practice calibration.	Included in normal clinic treatment
Aquasil Ultra Cordless B4 Pre-Impression Surface Optimizer	Enough for 30 impressions + 10 for practice calibration.	Included in normal clinic treatment
Aquasil Ultra Cordless Ultrathin intra sulcular tips	Enough for 30 impressions + 10 for practice calibration.	Included in normal clinic treatment
Aquasil Ultra PVS materials (heavy and light body)	Enough for 60 impressions + 10 for practice calibration.	Included in normal clinic treatment
GingiBraid retraction cord	12 containers- sizes: 00,0,1,2; (3) of each.	Included in normal clinic treatment
Hemodent	3 bottles + 1 for practice calibration	Included in normal clinic treatment
Viscostat	60 disposable vial/syringe	Included in normal clinic treatment
Impression trays	60 trays + 20 for practice calibration	Included in normal clinic treatment
Impression tray adhesive	3 bottles + 1 for practice calibration	Included in normal clinic treatment
Estimate Total:		

Timeline

The study is planned to last approximately 1.5 years to allow for recruitment and data collection and analysis. The study would ask the participants to come to 2 appointments; it might be possible to consent the patient and perform treatment on the same day, if the patient was scheduled for treatment that day already.

TO BE COMPLETED BY TREATING CLINICIAN:

Patient did not meet inclusion/exclusion criteria and is dropped from the study

Medical/smoking

Probing pocket depths around treatment tooth/teeth of greater than 4mm.

Bleeding on probing around treatment tooth/teeth.

The prepared finish line is greater than 1mm sub-gingival

Patient meets inclusion/exclusion criteria

Patient ID: _____

Impression Group: _____ *Corded* _____ *Cordless*

Clinic: _____ *Dental Faculty Practice*

_____ *Graduate Operative Clinic* _____ *1st* _____ *2nd* _____ *3rd*

_____ *Graduate Prosthodontic Clinic* _____ *1st* _____ *2nd* _____ *3rd*

Patient Age: _____

Gender: _____ *Male* _____ *Female*

Type of impression material used:

Tray adhesive used:

Aquasil Ultra Cordless

Aquasil Ultra

Yes *No*

Tray material:

Metal stock *Plastic stock* *Custom* *Plastic dual arch* *Metal dual arch*

Type of tray used:

Ant quad *Post quad* *Full arch*

Number of units requested:

2-3 FDP *Onlay* *Single crown x _____*

Anterior *Canine* *Premolar* *Molar*

Jaw: *Maxillary* *Mandibular*

Time Required for 1st Impression: _____ minutes and seconds

Number of Impressions Required to Obtain Adequate Impression: _____

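### A fixed block size of 4 per clinic, written in the protocol and used by unmasked clinicians, weakens the safeguard of opening the envelope only after tooth preparation

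*Combined protocol and SAP*

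**What the plan says.** The Methods section of the combined protocol and SAP stratifies by the three treating clinics and adds that "A block size of 4 within each stratum will be used to maintain a balanced allocation to impression group". The Materials and Methods paragraph of the abstract says the same. Neither place mentions varying the block size.

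On handling, Methods says: "Randomization allocations will be placed in sequentially numbered envelopes for ease of use by clinicians within the three clinics". On timing: "The treating clinician will open the allocation envelope after the tooth preparation is completed". The reason follows directly: "This is to limit the potential bias of the clinician altering the tooth preparation design in anticipation of a known gingival displacement technique".

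The clinician is unmasked by design, since he or she carries out the procedure and then documents it: "The clinician will record the impression technique, type of impression material used". Masking is planned only for the evaluators, in that "all of the images will be black and white so not to clue the examiners into which color of impression material was used".

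The treating clinician also checks eligibility and completes the form on which a patient is dropped. One ground on that form is a prepared finish line more than 1 mm below the gingival margin, which can be judged only once the tooth has been prepared.

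**The concern.** The plan itself treats anticipation of the technique as a source of bias, and its defence is late opening of the envelope. That defence works only while the contents cannot be deduced. With blocks always of 4 and two patients per arm in each, the last place in a block follows from the first three, and sometimes the third follows from the first two. If envelopes are numbered within a clinic, the number also shows the place in the block.

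Two decisions are exposed: how the tooth is prepared, and whether the patient is dropped on the finish-line criterion. The same clinician makes both. If either differed by expected arm, the arms would no longer be comparable on the impression errors that form a primary outcome. Black and white images cannot repair this, because they shield the evaluator and not the preparation or the retention of patients.

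**Working it through.** **The plan's own figure.** The documents give no figure for predictability. Their one design calculation is 30 per group (Statistical Analysis). Noether's formula reproduces it: (1.960 + 0.842)² / (3 × 0.209²) = 59.9 in total, or 30 per group. The present point does not affect it.

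**Inputs.** From Methods: block size 4, three clinics, 100 patients. The 1:1 ratio is inferred from the aim to "maintain a balanced allocation to impression group" and the equal groups of 30. Assumed where the documents are silent: envelopes numbered within clinic, about 33 patients per clinic, and how much of the earlier sequence a clinician sees.

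**Full knowledge, blocks of 4.** There are 6 equally likely sequences with two patients per arm.

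| Place in block | Certain | Best guess correct |
|---|---|---|
| 1 | 0 | 1/2 |
| 2 | 0 | 2/3 |
| 3 | 1/3 | 2/3 |
| 4 | 1 | 1 |
| Sum | 1.33 | 2.83 |

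- Certain: 1.33 / 4 = 33.3%.
- Best guess correct: 2.83 / 4 = 70.8%.
- Of 100 patients split 34/33/33, there are 8 complete blocks per clinic, so 24 × 1.33 = 32 certain allocations. Split 60/20/20, there are 25 blocks and 33.3 certain allocations.
- Guessing only when the block is unbalanced: such places number 1 + 1/3 + 1 = 7/3 per block, and the correct guesses at them 2/3 + 1/3 + 1 = 2. The rate is 2 / (7/3) = 85.7%.

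**Partial knowledge.** Let q be the chance that each earlier allocation in the block is seen, with the place known from the envelope number. An allocation is certain only when both members of a same-arm pair have been seen, so the certain share is q²/3.

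| q | Certain | Best guess correct |
|---|---|---|
| 1 | 33.3% | 70.8% |
| 0.75 | 18.8% | 64.6% |
| 0.5 | 8.3% | 59.9% |
| 0.25 | 2.1% | 55.4% |
| 0 | 0% | 50% |

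**Blocks of 4 and 6 in random order.** The certain share and overall accuracy were simulated with 33 patients per clinic and a guesser who knows the set of sizes and the full clinic history.

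| Measure | Fixed 4 | Mixed 4 and 6 |
|---|---|---|
| Certain | 32.3% | 5.6% |
| Correct, all patients | 70.2% | 68.5% |
| Correct, only when unbalanced | 86% | 81% |

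The last two rows can be checked by hand for complete blocks. A block of 6 yields 4.1 correct guesses overall. It has 3.8 unbalanced places, with 3.0 correct guesses at them. Mixing the two sizes equally gives (2.83 + 4.1) / 10 = 69.3% overall and (2 + 3) / (2.33 + 3.8) = 81.5% when unbalanced.

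**The case against.** The strongest reply is that full tracking is not in the documents. They do not give the number of clinicians per clinic, do not say that clinicians see each other's allocations, and do not say that clinicians are told the block size. What Methods describes them receiving is laminated clinical instruction sheets. Where several operators share a clinic, the certain share drops quickly, to about 8% at q = 0.5 and 2% at q = 0.25. This stands, and it makes one third an upper bound. It does not remove the point: the size is written in both the abstract and Methods, and no step to withhold it is stated.

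A reader might infer that fixed blocks defeat late opening altogether. They do not. Even under full tracking two thirds of allocations are not certain, late opening still withholds those, and the plan claims only to limit the bias.

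A reader might also expect varied blocks to end guessing. On either measure of accuracy the gain is small, provided that the overall rate is compared with the overall rate and the unbalanced-only rate with the unbalanced-only rate. Nor does variation remove every certain allocation if the set of sizes is known.

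Finally, drops must be tied to a listed criterion that the clinician records, which constrains selective retention. Fixed blocks of 4 are also a common choice in a small exploratory study. Both remarks are fair. They bear on how urgent the change is, not on whether it is worthwhile.

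**Conclusion.** The point holds as a weakness in concealment that is cheap to remove. A clinician with complete knowledge could be certain of about one third of allocations before preparing the tooth and guess about 71% correctly. At q = 0.5 the figures are about 8% and 60%. Where this trial would fall in that range cannot be read from the documents. The figures assume 1:1 blocks, envelopes numbered within clinic, and a clinician who knows the block size.

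A reader might go further and infer a particular bias in the error counts or a particular inflation of the type I error. The documents give nothing on which to base such a figure: no error rates by difficulty of case, no drop rates and no extent of tracking. The supported conclusion is that foreknowledge could affect the preparation or the finish-line drop decision, not that it did so or by how much. The change is advisable, and the sample size is untouched.

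**What to change.** Generate the schedule with block sizes varied at random within each clinic, for example 4 and 6. Remove the sizes from the abstract, Methods and anything given to clinicians, and leave them only with the person who prepares the schedule. Methods need say only that permuted blocks of varying, undisclosed size are used within clinic.

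The main gain is fewer certain allocations, about 32% down to about 6% even for someone who knows the set of sizes. Because guessing accuracy barely changes, withholding the sizes matters as well as varying them. The documents also do not state whether the envelopes are sealed and opaque; one sentence would settle that.

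The cost is re-generating one list. A clinic that stops mid-block could be out of balance by up to 3 patients (half of 6) rather than 2 (half of 4).

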Appendix B:

TO BE COMPLETED BY EVALUATORS

Evaluator: **ONE** **TWO**

Patient ID: _____

Errors in the finish line:

Voids/Bubbles Lack of wash material Tearing

Errors in the tray/material:

Cotton roll attached Inadequate fusion of viscosity Lack of polymerization

Show through of occlusal/incisal edges

Inadequate retention Pressure of tray on soft tissue Void on the preparation

Errors with gingival displacement/hemostasis:

Tissue over finish line Retraction cord attached Blood on impression

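### Nothing in the supplied text makes the clinician choose tray and adhesive before opening the allocation envelope, although some scored errors depend on that choice

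*Combined protocol and SAP*

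**What the plan says.** On allocation, the Methods section states: "The treating clinician will open the allocation envelope after the tooth preparation is completed". The reason given is to "limit the potential bias of the clinician altering the tooth preparation design in anticipation of a known gingival displacement technique". The safeguard is stated for the preparation only; tray and adhesive are not mentioned.

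On the tray, step 4 is worded the same in the corded and the cordless procedure: "An impression tray that has been filled with the heavy body consistency impression material is then placed over the arch of teeth". Neither procedure names a tray material, a tray type or the use of adhesive. The Methods section lists these among the things the clinician records: "whether tray adhesive was used; the tray material; the type of tray used". The clinician's form offers five tray materials, three tray types, and yes or no for adhesive.

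On the outcome, Appendix B has three groups of errors, one of them headed "Errors in the tray/material". The error count, from 0 to 13, is a primary outcome.

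On the analysis, the Statistical Analysis section makes an unadjusted Wilcoxon rank sum test primary. It also plans descriptive summaries of procedural materials by impression group, and a Poisson regression with clinic, jaw and procedural materials as covariates.

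The Methods section also requires clinicians to follow a laminated clinical instruction protocol, said to be in Appendix A. That protocol is not in the supplied text.

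**The concern.** The plan accepts that a clinician who knows the arm may change a discretionary step, and it shields one such step, the preparation. Tray and adhesive are also discretionary as far as the supplied text goes, and they come into use after the envelope is opened. If clinicians tended to pick a different tray or use adhesive differently in one arm, tray-related errors would differ between arms even if the two displacement methods performed equally. The total error count would then mix tray handling with gingival displacement, which is what the trial sets out to compare.

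The planned regression would not cleanly repair this. A tray chosen after opening may be a consequence of the arm. Adjusting for it then removes part of whatever the arm caused through the tray. It can also add bias if something unrecorded, such as a difficult site, affects both the tray chosen and the errors made.

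**Working it through.** **1. The plan's own figure.** The sample size is for the Wilcoxon test on total errors, with probability 0.709, 80% power and two-sided 0.05. By Noether's formula with equal arms, N = (1.960 + 0.842)² / [12 × 0.25 × (0.709 − 0.5)²] = 7.849 / 0.1310 = 59.9, or 30 per group. The stated figure reproduces. The Methods section plans 100 participants, so 50 per arm is also shown below.

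**2. Share of the score that is exposed.** Appendix B lists 3 finish-line, 7 tray/material and 3 displacement/hemostasis items: 3 + 7 + 3 = 13, which matches the stated range.
- Items that depend most directly on tray or adhesive: show-through of the tooth edges, inadequate retention, and tray pressure on soft tissue. 3/13 = 23%.
- Upper bound, if every item in the tray/material group counted: 7/13 = 54%. The other four (cotton roll, fusion of viscosities, polymerization, void on the preparation) are less evidently driven by the tray.

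**3. Timing.** The envelope is opened after preparation and the filled tray is seated at step 4. No passage places the choice of tray before or after opening. A choice made with knowledge of the arm is therefore permitted but not established.

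**4. Illustration A: net shift in errors.** None of these inputs is a finding about this trial.
- Errors per impression are Poisson with mean 0.82 in both arms. The mean is an assumption: −ln(1 − 0.56) = 0.82, the value at which 56% of impressions have at least one error. The 56% is the Background figure for inadequate impressions sent to laboratories, which is a different population and definition.
- The techniques are equal, but one extra tray error occurs in a stated fraction of one arm.
- Unadjusted two-sided Wilcoxon test at 0.05, 20,000 simulated trials per cell.

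| Net extra tray error in one arm | Mean 0.82, 30 per arm | Mean 0.82, 50 per arm | Mean 2, 30 per arm | Mean 2, 50 per arm |
|---|---|---|---|---|
| 0% | 5% | 5% | 5% | 5% |
| 5% | 5% | 6% | 5% | 5% |
| 10% | 7% | 8% | 6% | 6% |
| 20% | 13% | 18% | 8% | 10% |
| 30% | 22% | 35% | 12% | 17% |

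These are net differences between arms. A 20-point shift needs, for example, a 50-point difference in tray use and a 40-point rise in error risk with the less favourable tray (0.50 × 0.40 = 0.20).

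**5. Illustration B: difference in tray use.** Assume a 10% error rate per item, a less favourable tray that raises its affected items to 20% or 30%, and no displacement effect (3,000 trials per scenario). With three items affected:
- Less favourable tray used in 35% of one arm and 65% of the other: false-positive rate 6% to 10% at 30 per arm and 6% to 11% at 50.
- 20% against 80%: 8% to 22% at 30 per arm and 12% to 32% at 50.
- Equal use: about 4% to 5%.

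With all seven items affected, the rates at 30 per arm are 9% to 20% for 35% against 65%, and 27% to 65% for 20% against 80%. Those figures belong to the upper bound in step 2.

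**The case against.** The strongest case on the other side has four parts.

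- **A tray rule may exist.** The laminated protocol is mandatory for an impression to be included, and it is not in the supplied text. A rule on tray or adhesive there cannot be excluded. A form with several tray options and a yes/no for adhesive makes one less likely but does not settle it. This stands as a limit on the point.
- **Much is already balanced.** Step 4 is identical in both arms, clinicians are trained and calibrated on both procedures, and randomisation is stratified by clinic in blocks of four. Tray habits that differ between clinics should be roughly balanced. Only a habit that depends on the arm creates bias, and the documents give no evidence of one. This stands too.
- **The plan already looks at materials.** Summaries by arm would show an imbalance in tray use, the three error groups allow a difference confined to tray/material items to be seen, and the Poisson model includes procedural materials. A reader might infer that the plan ignores the matter; it does not. But a visible imbalance is not a removed one, the primary test remains unadjusted, and the adjustment is sound for tray and adhesive only if they are fixed before allocation is known.
- **Tray choice may be part of the technique.** Patients are randomised to an impression technique, so a pragmatic reading could count the tray as part of it. Against this, the aims concern displacement methods, and the common step 4 suggests that the tray was not meant to differ.

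A reader might also infer from the item count that more than half of the score is at the mercy of tray choice. Appendix B does not support that: 7 of 13 is an upper bound, and about three items depend directly on the tray.

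**Conclusion.** The point holds as a gap in a safeguard, not as a demonstrated bias. The supplied text lets a clinician who knows the arm choose tray material, tray type and adhesive. Three of 13 scored items, and at most seven, depend on that choice. The primary test does not adjust for it, and the planned adjustment is clean only if the choice precedes opening.

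It would go too far to say that the tray is chosen after allocation, that the choice is unrestricted, or that the error comparison is biased by a known amount. The documents give no timing for the choice, Appendix A's protocol cannot be checked, and neither the size nor the direction of an effect can be derived. The false-positive rates of about 5% to 22% (30 per arm) and 6% to 35% (50 per arm) rest on an assumed mean of 0.82 errors and assumed net shifts of 5% to 30%. They are near nominal at a 5% shift. At a mean of 2 errors with a 20% shift they are only about 8% and 10%. For an exploratory study this is a worthwhile, inexpensive improvement.

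**What to change.** Add to the allocation paragraph in Methods: the clinician selects tray material, tray type and adhesive and enters them on the clinician's form before opening the envelope; any later change is recorded with its reason. Move those fields ahead of the impression-group field, which now precedes them on the form.

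In the Statistical Analysis section, state that the pre-opening entries are the procedural-materials covariates for tray and adhesive in the Poisson model, whatever was finally used. They are then pre-randomisation values, balanced between arms on average. The log of later changes, reported by arm, shows how often knowledge of the arm could have mattered.

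This prescribes no tray. It costs a sentence in each section and a reordered form, and the tray is decided a few minutes earlier. If the clinical instruction protocol in Appendix A already contains a tray or adhesive rule, it should be reconciled with step 4 of the two procedures and with the options on the form.
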